## **12.0 DATA SECURITY:**

This study will utilize the secure, web-based, Research Electronic Data Capture (REDCap) system for data input. REDCap was developed by Vanderbilt University and is provided by Indiana University through their community license. REDCap is managed by the Indiana University Department of Biostatistics and secured by University Information Technology Services Advanced IT Core. Access to the password protected database will be limited to the investigators of this study, and any data that is distributed will be de-identified.

## **13.0 PARTICIPANT CONSENT:**

The protocol and informed consent form for this study must be approved in writing by the appropriate Institutional Review Board (IRB) prior to any participant being enrolled on this study.

Changes to the protocol, as well as a changes of principal investigator and study personnel, must also be approved by the Board. Records of the IRB review and approval of all documents pertaining to this study will be kept on file by the investigator (housed in the PI's Office) and are subject to inspection at any time during the study. Status updates will be submitted to the IRB as required by the board, as well as notification of completion of the study.

## **14.0 DATA SAFETY AND MONITORING:**

Although minimal risk is involved with this study, investigators will conduct continuous review of data and participant safety. Quarterly review meetings will be held and include the principal investigator,

clinical research coordinator and other members per principal investigator's discretion. Quarterly meeting summaries should include review of data, the number of subjects and responses observed. The meeting minutes and attendance will be kept on record from these meetings.

### **Adverse Event Reporting:**

Adverse events related to the study intervention will be captured throughout the study. All adverse events related to blood draw, gastrointestinal distress or allergic reactions to dried plums, or injuries associated with the physical function testing will be followed until resolution, a return to baseline, or deemed clinically insignificant.

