**Physical Activity Patterns.** Physical activity patterns will be assessed Visits 2-5 using the validated CHAMPS Physical Activity for Older Adults Questionnaire. This questionnaire is designed to elicit information on leisure, occupational, and home activities and classifies the activities based on duration. Participants will be asked to refrain from altering their physical activity from Visit 2 until the completion of the study at Visit 5. Physical activity data will be analyzed to determine usual activity level, consistency over time and deviations from baseline.

**Bowel Function and Gastrointestinal Tolerance.** At Visits 2 through 4, participants will be instructed to complete a validated questionnaire [50] about their bowel function and gastrointestinal tolerance each day throughout the treatment period. They will be asked to rate the severity of gastrointestinal symptoms—such as abdominal distention and nausea—on a 4-point scale (1 = absent, 2 = mild, 3 = moderate, 4 = severe). Participants will also record the date and time of each bowel movement. Stool consistency will be assessed using the Bristol Stool Scale, and ease of stool passage will be rated on a 5-point Likert scale (1 = very easy, 2 = easy, 3 = neither easy nor difficult, 4 = difficult, 5 = very difficult) [49].

**Dietary Assessment.** Prior to Visits 2-5, participants will enter their 3-day diet intake using ASA24 to include 2 weekdays and 1 weekend day. They will be instructed to measure (using standard measuring cups/utensils) and record all food, beverages and supplements consumed. At least two of the three days

should include the days immediately prior to their visit to coincide with fecal collections. [name], who is an RD, will assist with developing these instructions. Participants will be asked to refrain from making changes to their routine diet or supplement intake throughout the study. They will also be instructed to try to consume the same foods in the days preceding their final visit of each study period as they reported at baseline to minimize the influence of dietary factors on outcomes. The 3-day record will be analyzed by study personnel using the ASA24 tool. Dietary assessment will be performed to assess dietary pattern, energy intake, and macronutrient and select micronutrient composition.

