**Consumption of Dried Plums and Compliance.** The test product will be provided by the CA Dried Plum/Prune Board in commercially prepared snack bags. During the 1-week run-in to the dried plum intervention period, participants will be instructed to gradually increase their consumption of dried plum over 1 week following a schedule of 2 dried plums/d for 2 days (1 after breakfast and 1 after dinner), 4 dried plums/d for 3 days (1 after breakfast, 1 after lunch and 2 after dinner), followed by 6 dried plums/day (2 each after breakfast, lunch and dinner). Participants will be instructed to try to continue to spread the consumption of 50 g of dried plum throughout the day during the 4-wk intervention period and to consume their final dried plums at ~9:00 PM prior to their study visit. Suggestions will be provided with the assistance of [name] about ways to incorporate dried plums into the diet, without cooking. To assess compliance with the dried plum, each participant will be given a calendar to record the date and time that the fruit was consumed. The Study Coordinator will contact participants weekly by text or email to encourage compliance and note any adverse events. At the final visit, participants will return their calendar and any unused dried plum as indicators of compliance.

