### **Reporting to the IRB**

Unanticipated problems involving risks to participants or others will be reported **promptly** to the IRB if they:

- are unexpected;
- are related or possibly related to participation in the research; and
- suggest that the research places subjects or others at a greater risk of harm than was previously known or recognized.

If the serious adverse event does not meet all three (3) criteria listed above, the event does not have to be promptly reported to the Indiana University IRB. However, it will be reported at the time of continuing review.

**Prompt** reporting of unanticipated problems to the IRB is defined as within 5 days from becoming aware of the event.

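### The adverse-event capture rule in Section 14.0 is limited to intervention-related events, which is narrower than the weekly contact, the follow-up rule and the continuing-review rule it has to serve

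*Protocol*

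**What the plan says.** Section 14.0, Adverse Event Reporting, opens with the capture rule: "Adverse events related to the study intervention will be captured throughout the study". The sentence after it sets the scope of follow-up: "All adverse events related to blood draw, gastrointestinal distress or allergic reactions to dried plums, or injuries associated with the physical function testing" are to be followed until they resolve, return to baseline or are judged clinically insignificant.

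Section 8.0, in the paragraph on consumption of dried plums and compliance, adds a second route: "The Study Coordinator will contact participants weekly by text or email to encourage compliance and note any adverse events".

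The IRB part of Section 14.0 sets three criteria for prompt reporting, all of which must be met. One is that the events "are related or possibly related to participation in the research; and". It then provides: "If the serious adverse event does not meet all three (3) criteria listed above, the event does not have to be promptly reported" to the IRB. The next sentence closes the loop: "However, it will be reported at the time of continuing review".

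Two further sources of participant-reported information exist. Section 8.0 has women complete a validated questionnaire "about their bowel function and gastrointestinal tolerance each day throughout the treatment period", and the Section 7.0 schedule collects it at Visits 3 and 5. Section 8.0 also has the medical history updated at every visit after the first.

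**The concern.** A capture rule decides which events enter the record. If relatedness is judged first and recording follows, an event thought unrelated at first contact need not be written down, and nobody can reassess it later when a pattern appears. The quarterly review described in Section 14.0 can only look at what was recorded.

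The design makes this worse. The comparator is the absence of dried plum, and each woman knows which condition she is in. In a control period there is no intervention to which an event could be attributed, apart from possible carry-over in women who took plum first. A rule based on attribution therefore records readily in one condition and hardly at all in the other. At stake are the completeness of the safety record and whether event counts under plum and under control can be read side by side.

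**Working it through.** No arithmetic applies: the point depends on no rate, effect size or sample size. The check sets the provisions side by side.

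1. **Capture (Section 14.0, first sentence).** Scope: events related to the intervention. The word *only* is absent, but no other sentence in Section 14.0 widens capture.
2. **Follow-up (Section 14.0, second sentence).** Scope: plum-related complaints plus events from blood draws and physical function testing. The last two arise from study procedures, not from the intervention. An event cannot be followed to resolution unless it has been captured, so follow-up already reaches beyond the capture sentence.
3. **Weekly contact (Section 8.0).** Scope: any adverse event, with no relatedness filter. The sentence appears only under dried plum consumption and compliance. The protocol does not say whether the contact also runs in the control period or the washout.
4. **Prompt IRB reporting (Section 14.0).** Scope: related or possibly related, to participation in the research. This is wider than the capture sentence in two ways: it admits possible relatedness, and it covers participation as a whole, not just the intervention.
5. **Continuing review (Section 14.0).** A serious event escapes prompt reporting if it fails any one of three criteria. Being unrelated is one way to fail. Unrelated serious events therefore fall within the continuing-review rule, and reporting them presupposes that they were recorded.

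The fifth comparison is the sharpest. Staff who follow the capture sentence as written have no duty to record an unrelated serious event, yet the same section expects it to be reported later.

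Next, what offsets this:

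- **Gastrointestinal symptoms.** The daily questionnaire asks for severity and needs no judgement of cause. The Figure 1 caption calls both Phase 1 and Phase 3 treatment periods, and collection is scheduled at Visits 3 and 5, the ends of those periods. Read together, these cover both conditions.
- **Other events.** Medical-history updates at Visits 2 to 5 carry no relatedness filter and may recover some events. They are not described as adverse-event capture, and nothing says that their content feeds the adverse-event record.
- **Outcomes.** Section 3.0 lists no safety or tolerability outcome, so no listed endpoint depends on the capture rule.

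Finally, the start of the window. Physical function testing takes place at Visit 1 (Sections 6.0 and 7.0), and Section 9.0 provides for a small plum sample at the initial visit for women with certain known allergies. Recording that began at Visit 2 would miss events from both.

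**The case against.** The best case against is that this is only a matter of wording. The capture sentence does not say that other events are excluded, and its neighbour already takes in procedure-related events, which can occur under both conditions. The weekly contact and the medical-history updates are open to any event, so an unrelated serious event would probably come to light and could be reported. Section 14.0 describes the study as minimal risk, and no comparison of event rates is planned.

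Much of this stands. A reader might infer that the rule prevents a fair comparison of tolerability between plum and control. The documents do not support that: bowel and gastrointestinal effects, the product's main expected harm under Section 9.0, are rated daily without attribution in both periods. A reader might also infer that unrelated events are never captured, or that the continuing-review rule cannot be met. That too goes beyond the text, because two other routes could bring such events to notice.

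The inconsistency itself remains. Those routes sit outside the section that governs capture. One is not described as adverse-event recording, and the other may not run in the control period. Nor is this a detail that can be left to a statistical analysis plan: what is recorded, and when, is a protocol rule, and no later analysis can restore events that were not written down.

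**Conclusion.** The point holds as a real inconsistency in a stated rule, and it should be corrected. The capture sentence is narrower than the weekly contact, its own follow-up sentence, the prompt-reporting criterion and the continuing-review rule. In an open crossover against no plum, a capture rule that depends on attribution can lose events not at first recognised as related, and it leaves adverse-event counts not comparable between conditions.

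The limit on comparison concerns chiefly non-gastrointestinal events. The size cannot be given as a number, because the documents contain no event rates. The primary and secondary outcomes are not affected.

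The conclusion rests on two readings: that staff would take the capture sentence literally, since nothing in Section 14.0 widens it, and that the daily questionnaire is completed in both periods. If the second reading were wrong, the limit on comparison would extend to gastrointestinal events as well.

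**What to change.** Reconcile the capture sentence in Section 14.0 with the weekly contact in Section 8.0 and with the IRB text. State that:

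- all adverse events are recorded from Visit 1 to Visit 5, whatever their relatedness, and in the same way in both periods and the washout;
- the weekly contact runs under both conditions and in the washout, with the same question each time;
- relatedness and seriousness are judged after recording, and the IRB criteria are then applied unchanged.

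The cost is a wording change and a few more form entries. If the weekly contact does not now cover the control period and the washout, there will also be some additional texts or emails by the coordinator. No visit, sample or analysis changes.

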### **Reporting to the IRB**

Unanticipated problems involving risks to participants or others will be reported **promptly** to the IRB if they:

- are unexpected;
- are related or possibly related to participation in the research; and
- suggest that the research places subjects or others at a greater risk of harm than was previously known or recognized.

If the serious adverse event does not meet all three (3) criteria listed above, the event does not have to be promptly reported to the Indiana University IRB. However, it will be reported at the time of continuing review.

**Prompt** reporting of unanticipated problems to the IRB is defined as within 5 days from becoming aware of the event.

